	Evaluate the overall safety of deferasirox FCT formulation in patients with lower risk MDS at the beginning of their transfusional history	Overall safety, as measured by frequency and severity of reported AEs and SAEs and changes in laboratory values from baseline: serum creatinine, creatinine clearance ALT, AST, complete blood count (platelets, RBC and WBC) and total direct and indirect bilirubin).
	Leukemic transformation (including progression to leukemia or higher rIPSS scores)	Proportion of patients with a disease progression (progression defined as a transition into a higher MDS risk group based on revised IPSS scoring or progression to AML) Time to progression (defined as above) or to leukemia transformation.
	Hemopoietic response	Percentage of patients with hematologic improvements in term of erythroid response following IWG 2006 criteria. Time to reach transfusion dependence defined as > 2 PRBC units/months for 3 months for patients with pre-transfusional Hb < 9.0 g/dl (or <10 g/dl for patients with cardiac disease) or a total number of PRBC units received = 20 from baseline. Absolute reticulocytes count from baseline to every visit during the whole treatment period. Absolute values and evolution of serum transferrin receptor, GDF11, GDF15 and erythroferrone from baseline to every visit during the whole treatment period. Evaluation of transfusional ratio: number of units received in a

		
predetermined period/ mean pre-transfusional Hb level. Compared with other studies on general population (study and FISiM registry).
 
Patients receiving concurrent rHuEpo and other disease modifying agents will not be considered for hemopoietic response.

	Costs analysis	Cost and outcome with low dose in early chelation vs. chelation treatment in MDS patients with transfusional iron overload in accordance with either local or international guidelines
Exploratory	Study of biological cellular damage by iron toxicity before and during treatment	MDA values during the study and relationship to NTBI and LPI values

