Study design	
 • This is an open-label, single arm, phase II, study designed to look whether early intervention with low dose DFX improves clinical outcome of patients with MDS. • Efficacy of early - low dose DFX FCT to prevent iron accumulation regularly suppressing reactive oxygen species. • Safety of early low dose DFX FCT. • Exploratory: possibility to guide chelation therapy by NTBI/LPI. • One arm • Fixed dose • Blinding: Open • Structure: Single Group • Randomized: Non-randomized • A standard pre-transfusion Hemoglobin level will be indicated (Hb threshold for transfusion Hb 9 g/dl or 10 g/dl for patients with cardiac disease) to be maintained during the study year. Pre transfusion hemoglobin level and transfusions date and frequencies will be recorded. A transfusional ratio will be determined: number of units received in a predetermined period/ mean pre-transfusion Hb level 	
Duration of the study	Enrolment 1 year. Per protocol treatment: 1 year. Total duration 2 years	
Number of patients	60 (50 + 10 for 20% drop out rate)	
Population	Adult MDS patients (≥ 18 years). Very low, low and intermediate risk group by revised-IPSS. Regularly transfused patients with low PRBC transfusion burden (less than 2 units/months for 3 consecutive months) at beginning of their transfusion story (total number of PRBC units received 5-20). Patients should not meet the published criteria for transfusion dependency (2 PRBC units /month for three consecutive months).	
Inclusion criteria	
Study population:
 
 • Diagnosis: Adult Myelodysplastic Syndrome (≥ 18 years). • Revised IPSS: very low, low – intermediate. 	

	
 Having received 5-20 packed red blood cell units Serum ferritin ≥ 300 ng/ml Transferrin saturation $\geq 60\%$ Chelation naïve Capability to provide informed consent

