8.3. Current therapies for iron overload in lower risk MDS

Iron chelation therapy by deferasirox has been approved for low and intermediate-1 IPSS patients worldwide and its clinical benefit has been uniformly proved by several retrospective studies, prospective case control, registry and prospective (58) not randomized clinical studies. A recent meta-analysis confirmed the clinical value of iron chelation for lower risk MDS patients(59). A large, confirmatory Canadian prospective registry study (60) has been published after the meta-analysis publication. The prospective, randomized placebo control study is expected to provide definite information by the end of 2018 (ClinicalTrials.gov Identifier: NCT00940602).

Almost all the scientific societies published guidelines and regulatory agencies have indicated /approved chelation therapy in MDS after that a condition of chronic post transfusional iron overload has been achieved. Treatment is therefore determined by iron accumulation that is considered a mandatory prerequisite for iron toxicity (and not by iron toxicity per se). With minor variations, threshold for starting iron chelation has been identified adopting that in place for transfusion dependent thalassemia even though levels of accumulation historically associated with organ damage (based on data generated in the Thalassemias) are infrequent in MDS: 20 units of packed red blood cells and/or in a serum ferritin level of 1000 ng/ml (29,30) even if in real world clinical practice a higher threshold is common.

On the same basis indication to lower risk IPSS categories has been established on the idea that higher risk MDS patients live not enough to let dangerous iron accumulation (61).

Deferasirox has been proved to suppress toxic – redox active iron species even if the minimum necessary dose has not been explored (56,62,63).

Another iron chelator is actually approved worldwide for iron chelation in MDS: Deferoxamine, Desferal®. Deferoxamine modality of administration and half-life are not appropriate to patients with MDS. Another thalassemia licensed oral iron chelator (Deferiprone, Ferriprox®) is not approved in EU and US for MDS patients and limited MDS-literature is available (64).

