12.2. Exclusion criteria

- Patients aged <18 years old
- Higher risk MDS (Intermediate 2, high)
- Cumulative transfusional history of > 20 packed red cell units
- To be definitely classified as transfusion depended following published criteria (74) (having received 2 packed red cell units /months for three consecutive months)
- Creatinine Clearance (CrCL): <60 ml/min. Patients with CrCl of 40-60ml/min will be included only individually if no other renal risk factors are present.
- Serum creatinine $>2 \times$ ULN at screening.
- Serum creatinine will be measured at screening (repeatable)
- Significant proteinuria as indicated by a urinary protein/creatinine ratio > 0.5 mg/mg in a non-first void urine sample at screening (repeatable).

- ECOG performance status >2.
- Left ventricular ejection fraction < 50% by echocardiography
- A history of hospitalization for congestive heart failure.
- Systemic diseases which would prevent study treatment (e.g. uncontrolled hypertension, cardiovascular, renal, hepatic, metabolic, etc.)
- Clinical or laboratory evidence of active Hepatitis B or Hepatitis C (see EASL criteria).
- History of HIV positive test result (ELISA or Western blot).
- Treatment with systemic investigational drug within 4 weeks or topical investigational drug within 7 days of study start.
- ANC < 500/ microL
- Platelets transfusion dependency
- ALT or AST >3 x ULN at screening.
- Total bilirubin >1.5x ULN at screening (patients with Gilbert syndrome are allowed to enter the study).
- Diagnosis of liver cirrhosis child score C.
- Patients participating in another clinical trial other than an observational registry study.
- Patients with a history of another malignancy within the past five years, with the exception of basal skin carcinoma or cervical carcinoma in situ or completely resected colonic polyps carcinoma in situ.
- History of non-compliance to medical regimens, or patients who are considered potentially unreliable and/or not cooperative.
- Presence of a surgical or medical condition which might significantly alter the absorption, distribution, metabolism or excretion of study drug.
- Pregnant, intending-to-become pregnant, or breast-feeding patients.
- Women of potential maternity age who do not agree to practice effective contraceptive methods for the entire study duration.
- History of drug or alcohol abuse within the 12 months prior to enrollment.
- Hypersensitivity to the active substance or to any of the excipients.

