15. REMOVAL OF SUBJECTS FROM TREATMENT AND/OR STUDY

15.1. Discontinuation from study treatment

Patients may voluntarily discontinue from the study treatment for any reason at any time.

If a patient decides to discontinue from the study treatment, the investigator should make a reasonable effort (e.g. telephone, e-mail, letter) to understand the reason for this decision and record this information in the patient's chart and on the appropriate CRF pages.

Patients may be considered withdrawn if they state an intention to withdraw, fail to return for visits / lost to follow-up for any other reason.

The investigator should discontinue study treatment for a given patient if, he/she believes that continuation would be detrimental to the patient's well-being.

Study treatment must be discontinued under the following circumstances:

- Death
- Adverse Events
- Abnormal laboratory value
- Pregnancy
- Unsatisfactory therapeutic effect
 - patients with evident inadequate chelation (Transfusion burden > 4 units/month over a three consecutive months period and > 1 PRBC unit/week and a total number of PRBC received >20) the protocol will be discontinued and the patient will be treated as clinically (by label) indicated
- Unwillingness to comply with study procedures/treatment as per protocol
- Discovery of patient ineligibility
- Intake of prohibited medications
- Protocol violation
- Consent withdrawal
- Lost to follow-up
- Administrative problems
- Premature termination of the study
- In patients with serum ferritin <300 ng/ml therapy will be suspended and the patient will remains in study, with the same transfusion (minimal Hb level 9 g/dl) and study criteria. Patients will restart treatment as soon as serum ferritin arise >300 ng/ml.

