	Hemopoietic response	Percentage of patients with hematologic improvements in term of erythroid response following IWG 2006 criteria. Time to reach transfusion dependence defined as > 2 PRBC units/months for 3 months for patients with pre-transfusional Hb < 9.0 g/dl (or <10 g/dl for patients with cardiac disease) or a total number of PRBC units received = 20 from baseline. Absolute reticulocytes count from baseline to every visit during the whole treatment period. Absolute values and evolution of serum transferrin receptor, GDF11, GDF 15 and erythroferrone from baseline to every visit during the whole treatment period. Evaluation of transfusional ratio: number of units received in a

		predetermined period/ Mean pre-transfusional Hb level. Compared with other studies on general population (study and FISIM-ETS registry). Patients receiving concurrent rHuEpo will not be considered for erythroid response
	Costs analysis	Cost and outcome with low dose in early chelation vs. chelation treatment in MDS patients with transfusional iron overload in accordance with either local or international guidelines
Exploratory objective and endpoint	Study of biological cellular damage by iron toxicity before and during treatment	MDA values during the study and relationship to NTBI and LPI values

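### Erythroid response drops patients who receive rHuEpo after baseline, with a scope that differs between sections; as a minor point, time to transfusion dependence mixes a rate with a 20-unit count

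*Combined protocol and SAP*

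**What the plan says.** **Erythroid response.** Section 14.5 permits concomitant rHuEpo, has it recorded, and states that patients given it in the course of the study year are not evaluated for erythroid response. The hemopoietic-response row of section 17.2.2 likewise leaves concurrent rHuEpo users out of erythroid response. The same row in the synopsis goes further: it adds other disease-modifying agents and removes these patients from hemopoietic response as a whole. Section 20.3 defines the full analysis set (FAS) as all enrolled patients and assigns efficacy parameters to the FAS and the per-protocol set. No section says how the excluded patients are counted.

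**Time to transfusion dependence.** Section 17.2.2 gives two alternative ways to have the event. One is a rate: "> 2 PRBC units/months for 3 months for patients with pre-transfusional Hb < 9.0 g/dl" (with a higher Hb limit in cardiac disease). The other is a count: "a total number of PRBC units received = 20 from baseline". The synopsis has the same count. The entry exclusion in section 12.2 defines dependence by rate alone, at a slightly different level: "having received 2 packed red cell units /months for three consecutive months". The synopsis describes the population as "Regularly transfused patients with low PRBC transfusion burden (less than 2 units/months for 3 consecutive months".

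**The concern.** Starting rHuEpo during the year is a post-baseline event, and it may well be prompted by poor erythroid function. Dropping those patients conditions the response rate on what happened after treatment began. The result describes a group that cannot be identified at baseline, and it is not an analysis of all enrolled patients. The conflict over scope makes this worse: on the synopsis wording a patient leaves every hemopoietic endpoint, including time to transfusion dependence, while on the wording of 14.5 and 17.2.2 the same patient leaves only erythroid response. Two analysts could follow the plan and report different denominators.

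The second, smaller matter is that the count component measures cumulative load. A patient can be recorded as becoming dependent without any rise in transfusion rate, and the composite alone does not show which component produced the event.

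**Working it through.** The plan states no expected response rate, rHuEpo use, event rate or power for these endpoints, so there is no planned figure to reproduce.

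**1. Erythroid response**

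Inputs: 60 patients planned (section 11.2), FAS = all enrolled (20.3). Assumed, because the documents give neither: 10 responders, no rHuEpo at baseline, and 12 or 18 on-study starters.

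- All kept: 10/60 = 16.7%.
- 12 starters dropped, all non-responders: 10/(60 − 12) = 10/48 = 20.8%.
- 18 starters dropped, all non-responders: 10/(60 − 18) = 10/42 = 23.8%.
- 12 dropped, 2 of them responders: (10 − 2)/48 = 8/48 = 16.7%, no change.
- 12 dropped, 4 of them responders: (10 − 4)/48 = 6/48 = 12.5%, a fall.

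When all starters are non-responders, dropping a share *e* of patients multiplies the rate by 1/(1 − *e*): 1.25 at 20%, 1.43 at 30%. The direction depends on who starts.

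**2. Scope of the exclusion**

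| Section | Agents | Endpoints lost |
|---|---|---|
| Synopsis, hemopoietic response | rHuEpo and other disease-modifying agents | all hemopoietic response |
| 14.5 | rHuEpo | erythroid response |
| 17.2.2 | rHuEpo | erythroid response |

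**3. Transfusion dependence**

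Rate needed to reach 20 units in the 12-month treatment period (section 11.3): 20/12 = 1.67 units a month.

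A repeating 2-2-1 pattern accumulates 2, 4, 5, 7, 9, 10, 12, 14, 15, 17, 19, 20, so the event falls at month 12. No month exceeds 2 units, and every three-month total is 5. The patient therefore meets neither the rate component nor the 12.2 exclusion, whether these are read month by month or as a three-month total.

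For steady patients the effect is confined to about 1.67 to just under 2 units a month. At 1.5 a month, 20/1.5 = 13.3 months, beyond the study year.

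How many events come from the count alone depends on how the rate component is read. Simulation assumptions: 400,000 patients per rate, constant Poisson rate, 12 months, Hb condition met, count event at 20 or more units, no screening against the entry criteria.

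| Units per month | Composite; share from count only, if at least 3 units in each of 3 consecutive months | Composite; share from count only, if more than 6 units in any 3 consecutive months |
|---|---|---|
| 1.0 | 2.4%; 80% | 20%; 0.4% |
| 1.5 | 36%; 84% | 67%; 1.4% |
| 1.8 | 67%; 79% | 86%; 1.2% |

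At 1.0 unit a month, the reading alone moves the composite from 2.4% to 20%.

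**The case against.** **Exclusion as an evaluability rule.** The strongest reply is that the rHuEpo rule is deliberate. It stops an erythropoietic drug's effect from being credited to deferasirox, and an endpoint-specific rule can be read as a restriction within the FAS. The text speaks of not evaluating or not considering these patients and never mentions a denominator. The purpose stands. It does not settle the matter, because the plan never names such a subset, and the same purpose can be met without dropping patients on a post-baseline event. Counting starters as non-responders is one defensible choice among several, which is why the present rule should stay as a sensitivity analysis.

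**The 20-unit count as a milestone.** Section 8.3 cites "20 units of packed red blood cells and/or in a serum ferritin level of 1000 ng/ml" as a threshold for starting chelation, so the count has a clinical basis. This stands, and it is why the composite should be kept. It is also true that if the synopsis burden limit means at most one unit in every month, a steady patient receives at most 12 units in the year and the effect vanishes.

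**Two stronger readings that the documents do not support.** A reader might infer that most dependence events would be artefacts of the count. That holds only under the each-month reading; under the three-month-total reading the share is about 1% or less, and the simulated patients were not screened for eligibility. A reader might also take the 20 units as a lifetime total, since the synopsis uses similar words at entry, "at beginning of their transfusion story (total number of PRBC units received 5-20", and section 15.1 has "a total number of PRBC received >20" with no start point. But the endpoint says the count runs from baseline, section 15.1 is a discontinuation rule and not this endpoint, and under a lifetime count a patient entering with 20 units would have the event on day 0.

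**Conclusion.** The concern holds for erythroid response. The evaluated group depends on rHuEpo received after baseline, this sits badly with efficacy analysis on all enrolled patients, and the scope of the exclusion is contradictory between the synopsis and sections 14.5 and 17.2.2. The illustrative shift is from 16.7% to between 20.8% and 23.8%, resting on 10 assumed responders and 12 to 18 assumed non-responding starters out of 60. One might conclude that the reported rate will be too high. The documents do not show that: they give no rHuEpo use and no response rate, and other equally possible splits leave the rate unchanged or lower it.

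The transfusion-dependence point is minor. The count component can record an event without a change in rate, but its weight cannot be stated until the rate wording is settled.

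All of this concerns secondary endpoints of a single-arm phase II study. The primary liver-iron endpoint is untouched.

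**What to change.** **Erythroid response**

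1. State one scope for the exclusion, naming the agents and the endpoints, and use it in the synopsis, 14.5 and 17.2.2.
2. Exclude only patients already on a listed agent at baseline, and define those who remain as a named subset of the FAS.
3. Keep patients who start any listed agent on study in the denominator. Count them as responders only if the IWG 2006 criteria were met before the start date, otherwise as non-responders. This covers the other disease-modifying agents too, if they are listed.
4. Report the current exclusion rule as a sensitivity analysis.

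**Transfusion dependence**

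5. Keep the composite, but report time to the rate criterion and time to 20 units from baseline separately, and do not interpret count-only events as worsening.
6. Reconcile the rate wording of 17.2.2 (more than 2 units, 3 months) with that of 12.2 (2 units, three consecutive months), and say whether it applies to each month or to the three-month total.

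**Cost.** Text changes and a little extra analysis. Sections 11.1 and 14.5 already have transfusion dates and rHuEpo use recorded; start dates of any other listed agent should be available from the concomitant-medication record (section 16.6). The downside is a possibly lower response rate. For example, if there are 18 starters and 3 of 10 responders respond only after starting, the current rule gives 7/42 = 16.7% and the proposed rule 7/60 = 11.7%. No dependence events are lost.

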11. STUDY DESIGN

11.1. Overview of study design

[figure not shown]
This is an open label, single arm, phase II, study.

The study includes a screening period (in which patients eligibility will be assessed) followed by a 1-year treatment period during which monthly visits will take place to evaluate safety and efficacy parameters (total 16 visits + 1 screening visit).

Study treatment with low dose (3.5 mg/kg/day) DFX-FCT will be given to all enrolled patients at the beginning of their transfusional history

Dose activity will be monitored by regular NTBI /LPI suppression and by prevention of iron accumulation as demonstrated by hepatic iron concentration, comparing baseline versus end of study iron concentration. It has been clearly demonstrated that liver iron concentration is proportional to total body iron stores (LIC x 10.6 = total body iron store in mg/kg)(39)

A standard pre-transfusional Hemoglobin level will be indicated (Hb threshold for transfusion Hb 9 g/dl or 10 g/dl for patients with cardiac disease) to be maintained during the study year. Pre transfusional hemoglobin level and transfusions date and frequencies will be recorded. A transfusional ratio will be determined: number of units received in a predetermined period/ mean pre-transfusional Hb level

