12. STUDY POPULATION

12.1. Inclusion criteria

- Diagnosis: adult Myelodysplastic Syndrome (≥ 18 years).
- Revised IPSS: very low, low – intermediate.
- Having received 5-20 packed red blood cell units
- Serum ferritin >300 ng/ml
- Transferrin saturation $>60\%$
- Chelation naïve
- Ability to provide informed consent.

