14.4.5. Contraception

Non-sterilized female patients of reproductive age group and male patients should use effective methods of contraception through defined periods during and after study treatment as specified below.

Female patients must meet 1 of the following:

- Postmenopausal for at least 1 year before the screening visit, or surgically sterile, or
- If they are of childbearing potential, agree to practice 2 effective methods of contraception from the time of signing of the informed consent form through 6 months after the last dose of study drug (since Deferasirox can reduce the effectiveness of hormonal contraceptives, it is recommended that women of childbearing age use additional or alternative non-hormonal contraceptive methods), or
- Agree to practice true abstinence, when this is in line with the preferred and usual lifestyle of the subject. (Periodic abstinence [e.g., calendar, ovulation, symptothermal, post ovulation methods] and withdrawal are not acceptable methods of contraception.)

14.5. Excluded/admitted concomitant medication.

Admitted concomitant medication: as per clinical practice. Concomitant rHuEpo is admitted and registered (patients who receive rHuEpo during the year study will not be evaluated for erythroid response). No additional experimental therapy is admitted.

A standard pre-transfusion Hemoglobin level will be indicated (Hb threshold for transfusion Hb 9 g/dl or 10 g/dl for patients with cardiac disease) to be maintained during the study year. Pre transfusion hemoglobin level and transfusions date and frequencies will be recorded.

A transfusional ratio will be determined: number of units received in a predetermined period/ mean pre-transfusion Hb level.

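### The transfusional ratio is to be compared with an unmatched general population, although trial patients are selected on its numerator and transfused to a protocol-set Hb trigger, so a difference cannot be read as a drug effect

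*Combined protocol and SAP*

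**What the plan says.** Section 11.1 defines the measure: "A transfusional ratio will be determined: number of units received in a predetermined period/ mean pre-transfusional Hb level". The length of the period is not given. Section 17.2.2 places the ratio under hemopoietic response and names the comparator: "Compared with other studies on general population (study and FISIM-ETS registry". The Synopsis says the same: "Compared with other studies on general population (study and FISiM registry".

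The entry rules act on the numerator of that ratio:

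- Section 12.1 requires "Having received 5-20 packed red blood cell units".
- The Synopsis describes the population as having "low PRBC transfusion burden (less than 2 units/months for 3 consecutive months) at beginning of their transfusion story".
- Section 12.2 excludes patients already classed as transfusion dependent, "having received 2 packed red cell units /months for three consecutive months".

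Transfusion practice is also set by the protocol. Section 14.5 states "A standard pre-transfusion Hemoglobin level will be indicated (Hb threshold for transfusion Hb 9 g/dl or 10 g/dl for patients with cardiac disease", and Sections 11.1 and 20.1 repeat this.

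The study has a single arm (Section 20.1). For secondary endpoints, Section 20.3 offers only a choice between parametric and non-parametric tests. No section gives the comparator's eligibility, transfusion-dependence mix, Hb trigger, index date, follow-up window or rHuEpo use.

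**The concern.** An external comparison without a concurrent control is informative only if the two groups would have had similar values without the drug. Here they would not be expected to. Entry conditions on recent and lifetime units, and units received form the numerator. The denominator depends on a transfusion trigger that the trial fixes and that the comparator need not share.

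This is more than missing detail, because the comparator that is named is itself unsuitable. The Synopsis and Section 7 say that the study asks whether early low-dose treatment improves clinical outcome. A ratio below that of the registry could readily be reported as a hemopoietic benefit when it reflects who was enrolled and how they were transfused. A ratio above it could equally hide a benefit.

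**Working it through.** The plan states no figure for the ratio, so there is none to reproduce.

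**Inputs from the documents:** the ratio definition and the 9 or 10 g/dl trigger (Section 11.1), 5 to 20 units (Section 12.1), under 2 units a month (Synopsis), and the dependency exclusion (Section 12.2). **Assumed:** a 12-month period, taken from the treatment year, and every comparator transfusion rate and trigger below.

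**1. Value implied by the entry limit.** Ratio = 12 × units per month ÷ mean pre-transfusion Hb. A patient who stays below 2 units a month stays below 24/9 = 2.67, or 24/10 = 2.40 at the cardiac trigger.

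**2. Extreme contrast at equal Hb (9 g/dl).**
- Entrants staying at 1 to 1.9 units/month: 12/9 = 1.33 to 22.8/9 = 2.53.
- Comparator at an assumed 3 to 4 units/month: 36/9 = 4.00 to 48/9 = 5.33.
- Fold difference: 4.00/2.53 = 1.6 to 5.33/1.33 = 4.0. Hb cancels, so these are 3/1.9 and 4/1.

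This makes every comparator patient transfusion dependent and holds every entrant at the entry rate. It is an illustration, not an estimate.

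**3. Mixed cohorts with no drug effect and the same Hb throughout.** Simulation of 400,000 patients per scenario. Monthly units are Poisson with a gamma-distributed patient rate. Dependency means at least 2 units in each of three months. Prior history adds 0 to 9 further months. Trial-eligible patients are those not dependent with 5 to 20 units so far. The entries show the trial-eligible mean 12-month ratio relative to the comparator's.

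| Assumed mean units/month (gamma shape) | vs cohort with ≥5 units | vs unrestricted, 0% never transfused | 30% never transfused | 50% never transfused |
|---|---|---|---|---|
| 1.0 (1) | −24% | +21% | +73% | +143% |
| 1.0 (2) | −13% | +15% | +64% | +130% |
| 1.5 (1) | −37% | −9% | +30% | +82% |
| 1.5 (2) | −24% | −8% | +32% | +85% |
| 2.5 (1) | −52% | −39% | −13% | +22% |
| 2.5 (2) | −40% | −33% | −5% | +33% |

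Against a cohort with at least 5 units that includes dependent patients, selection alone lowers the trial's ratio in every scenario, by 13% to 52%. As a fold difference this is 1/0.87 = 1.15 to 1/0.48 = 2.1. Against an unrestricted cohort the sign changes.

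**4. Trigger.** With identical units, the change in the ratio is comparator Hb ÷ trial Hb − 1.
- 9 in the trial against 8: 8/9 − 1 = −11.1%.
- 10 against 8: 8/10 − 1 = −20.0%.
- 9 against 10: 10/9 − 1 = +11.1%.

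Holding a higher Hb also calls for more units. For 9 against 8, 9/8 − 1 = 12.5% more units cancels the effect. The comparator's trigger is not given, so the net sign is unknown.

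**The case against.** A reader might infer that the trial is bound to look better than the registry even if the drug does nothing. The documents do not support that:

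- The minimum of 5 units also removes patients who are rarely transfused, and this pushes the other way.
- The trigger acts on numerator and denominator together, against an unstated comparator trigger.
- Section 8.1 says that most MDS patients eventually become transfusion dependent. That describes the course of the disease, not the make-up of the registry in any comparison window.
- Entrants need not stay at their entry rate. Time to transfusion dependence is itself an endpoint in Section 17.2.2.

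All of this stands. One reply narrows it. A never-transfused patient has no pre-transfusion Hb, so a patient-level ratio is undefined, and the largest upward figures in the table need a cohort-level ratio. Even with no never-transfused group, however, the unrestricted comparison runs from 39% lower to 21% higher.

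It can also be said that the ratio is one item in one secondary objective. IWG 2006 erythroid response is listed first, and the ratio has no success threshold. That is correct and limits the weight of the point. Finally, nothing forbids choosing a similar registry subset. Nothing requires it either, and the wording points to a general population.

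**Conclusion.** The point holds as one of confounding. The planned comparison mixes any drug effect with eligibility and transfusion practice, and no provision in the plan separates them, so it cannot support a claim of hemopoietic benefit.

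Bias in the drug's favour is likely if the comparator includes transfusion-dependent patients. Its direction and size cannot be fixed from the documents. Under the assumed rates it is about 13% to 52% against a mixed transfused cohort with at least 5 units. The 1.6- to 4.0-fold figure applies only to the extreme case of an all-dependent comparator at 3 to 4 units/month and equal Hb. These sizes rest on assumed rates and a 12-month window. The conclusion that the difference cannot be attributed to the drug does not rest on them. The primary LIC endpoint is unaffected.

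**What to change.** In Section 17.2.2, the Synopsis and Section 20.3:

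- Replace the general population with registry patients who meet this trial's transfusion and disease entry rules: revised IPSS very low to intermediate, 5 to 20 units, below the dependency rate, chelation naive, and the ferritin and transferrin saturation limits where recorded.
- Index each comparator patient at the date these rules are first met and follow for 12 months whatever the later transfusion need. State that the ratio's period is the same 12 months in the trial.
- Compare within bands of pre-transfusion Hb.
- Apply one rHuEpo rule to both groups. The Synopsis removes users of rHuEpo and other disease-modifying agents from hemopoietic response as a whole, whereas Sections 14.5 and 17.2.2 remove rHuEpo users from erythroid response only. These must be reconciled first, since they decide who enters the ratio.
- Label the result descriptive.

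If the registry does not hold the needed fields, which the documents do not describe, drop the external comparison and report only the within-patient ratio by period.

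The cost is a filter and an index date on a registry that the plan already names, some rewording, and fewer comparator patients.
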